Primary Analysis for Aim 1: “Does randomization to different resuscitation strategies cause a difference in cognitive function, unbiased by differences in mortality-based selection?” Differential mortality can lead to misleading analyses of the impact of treatment on outcomes. This has been termed “selection bias”(86), “informative censoring,” or “censoring of the extreme phenotype”.(87) There is no universally accepted solution to this problem. We propose the approach of Permutt and Li of the Office of Biostatistics at the U.S. Food and Drug Administration and also endorsed by recent NHLBI-sponsored review.(88) This approach recognizes that death is extremely poor cognitive function, just not assessed on the same numeric scale as the MoCA-Blind or HSCT. This approach will be used for the primary analysis using MoCA-Blind, and an executive function-specific secondary analysis using HSCT.

The method of Permutt and Li calculates an empirical cumulative distribution function (ECDF) for the fraction of patients with cognitive impairment, considering all possible dichotomizations of the cognition scores (including informative non-response due to poor cognition and death as the most extreme forms of poor cognition).

Measuring Potential Mediators in SHAMROC. All will be collected as part of the CLOVERS CRF.	Permutt and Li thereby avoid loss of information and the controversy associated with selecting a single cut-point (ie , with the Rankin scale), while giving an interpretable summary statistic. Permutt and Li demonstrate that the mean outcome scores among the better performing patients from each study arm (“trimmed means”) are efficient statistics for reporting the between-group differences using the intention to treat principle. They recommend trimming each trial arm equally,
Days of mechanical ventilation in the first 28 after randomization will be measured, as will the development of ARDS in first 7 days. (Aims 1 & 2)	
Severity of hypoxemia will be measured as the lowest routinely obtained pulse oximetry saturation on the daily logs, obtained during the first 7 days in the ICU. (Aim 1)	
Renal failure will be defined by the KDIGO staging system (serum creatinine criteria only (89)) between baseline and 7 days to assess for de novo or worsening acute kidney injury. As treatment assignment could impact urine output, we will use only the creatinine criteria.(90) Patients on chronic dialysis will be ineligible for this analysis. (Aims 1 & 2)	
Net fluid balance will be defined as a proportion change in body weight compared to admission, as in (18). (Aim 2)	

just above the expected overall rate of death and non-response. In SHAMROC, 33% of each study arm will be “trimmed.”

Under this trimming, the test statistic has a straightforward interpretation: “How large of a difference in average cognitive function is caused by randomization to wet versus dry resuscitation, measured in the better-off ⅔ of patients?” Permutt and Li developed a permutation test for the confidence interval for this test statistic under no assumptions other than randomization, which is particularly appealing given the often-skewed distributions of cognitive function scores. We will report both the test statistic (with 95% CI) and graphically present the ECDF curve for each randomized group to summarize all data.

If necessary due to missing data in the electronic case report form (CRF)—which is not expected—we will use a Bayesian implementation of the model to impute missing values nested within sites, using a Gibbs sampler to impute from the posterior of the missing data given observed data.(91-95)

Mediation Analysis for Mechanism.

We hypothesize that differences in cognitive outcome between wet and dry resuscitation may stem from differences in rates of intervening organ dysfunctions and hypoxia. Respiratory dysfunction may harm the brain by either hypoxemia, exposure to delirigenic medications and practices,(96) or systemic effects of ventilator-induced lung injury.(97) Renal dysfunction may harm the brain by escalating inflammation (98) and multiple organ dysfunction, progression to chronic kidney disease,(99) uremia, or exposure to dialysis (“dialysis brain” or “hemodialysis fatigue syndrome” (100)). Hypoxemia was a major independent predictor of poor outcome in ACOS.(11, 101, 102)

To test mediation if there is a difference between treatment groups, we will generalize the primary analysis. Permutt and Li demonstrate that analysis of covariance (ANCOVA) can be used to estimate the trimmed mean test statistic, adjusting for a potential mediator. This is repeated on each of the permuted datasets to develop confidence intervals. This allows us to assess—one-by-one for each potential mediator—the magnitude of the difference in average cognitive function between wet and dry treatment arms explained by each mediator.

Analysis for Aim 2: “Does randomization to different resuscitation strategies cause a difference in physical disability, unbiased by differences in mortality-based selection?”

Paralleling our approach in Aim 1, we will use the method of Permutt and Li to assess: “How large of a difference in average physical disability is caused by randomization to wet versus dry resuscitation, measured in the better-off two-thirds of patients?” Death will be considered as an extreme form of physical disability, and permutation tests will be used to calculate a confidence interval for this test statistic under no assumptions other than randomization. We will report both the test statistic (95% CI) and graphically present the ECDF curves by randomized group.

Mediation Analysis for Mechanism. Similar to effects on cognitive impairment, we hypothesize that initial resuscitation strategy may affect disability outcomes through a number of key pathways. We will focus on respiratory failure, renal failure, and persistent hypervolemia as potential mediating factors. Respiratory failure is consistently associated with post-ICU disability, with likely contributions from immobility, increased days of delirium/coma due to sedation, higher levels of inflammation, and longer duration of hospitalization. Loss of muscle

mass, for example, is accelerated in patients with respiratory failure and shock(115). It is possible that acute respiratory failure and mechanical ventilation will be more common in the wet resuscitation strategy arm because of increased pulmonary edema. Renal failure may differ between study arms and is another factor frequently associated with physical impairment after critical illness, with increased incidence of muscle loss and weakness.(115, 116) The 2 resuscitation strategies will have significant differences in fluid balance, particularly among patients with shock persisting past the first 4 hours.

Paralleling Aim 1, we will use Permutt and Li's ANCOVA to answer: "How large of a difference in average physical disability is caused by randomization to wet versus dry resuscitation, measured in the better-off $\frac{2}{3}$ of patients, controlling for differences in the hypothesized mediator?" We will also report the fractional reduction of the unadjusted effect that is associated with each hypothesized mediator.

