2.4 Study Design

Study Design: Multicenter, prospective, phase 3 randomized non-blinded interventional trial of fluid treatment strategies in the first 24 hours for patients with sepsis-induced hypotension.

1. We will emphasize early screening and protocol initiation, and enroll a maximum of 2320 patients with suspected sepsis-induced hypotension.
 - ✓ All patients will receive at least 1 liter of fluids prior to meeting study inclusion criteria (and no more than 3 liters prior to randomization).
 - ✓ Patients will be enrolled within 4 hours of meeting study inclusion criteria
 - ✓ Balanced crystalloid solution (such as lactated Ringers, Hartman's solution, Plasmalyte or Normosol) recommended
2. Restrictive Fluids (Early Vasopressors) Group (See Protocol Schema Appendix A)
 - ✓ Norepinephrine will be used as preferred vasopressor and titrated to achieve mean arterial pressure (MAP) between 65 mmHg and 75 mmHg
 - ✓ "Rescue fluids" recommended as 500 ml boluses if predefined rescue criteria are met
3. Liberal Fluids (Fluids First) Group (See Protocol Schema Appendix A)
 - ✓ Additional 2-liter intravenous fluid infusion upon enrollment with a clinical evaluation at the end of the first liter
 - ✓ Administer 500 ml fluid boluses for fluid triggers until 5 liters administered (includes BOTH pre-randomization and post-randomization intravenous fluids), or development of clinical signs of acute volume overload develop
 - ✓ Return to care without study guidance after 5 liters of fluid (this includes BOTH pre-randomization and post-randomization intravenous fluids) are administered

“Rescue vasopressors” recommended for persistent hypotension/hypoperfusion and acute volume overload, if other “rescue” criteria are met, or if the judgment of the clinical team is that vasopressors are thought to be in the best interest of the patient during fluid administration to support blood pressure and then weaned off as feasible once the fluid boluses have had their effect.

4. Attending physician and clinical provider oversight
 - ✓ The attending physician must agree that both the CLOVERS Early Vasopressor and Fluid First approaches are consistent with good medical care for their patient prior to enrollment.
 - ✓ The attending physician will be informed that fluids or vasopressors can be used at any time if they are thought to be in the best interest of the patient.
5. Other care

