2.11 Sample Size/Interim Monitoring

1. Randomization 1:1; two-sided alpha 0.05.
A total of 2320 patients are needed to detect a 4.5% absolute mortality difference between treatment groups with 90% power assuming 15% mortality in the liberal fluids group. The principal analysis will be intent-to-treat, based upon randomization assignment.
2. There will be a protocol feasibility assessment phase at the approximately 100-patient mark, and then after approximately 100 enrolled patients are available after any protocol changes for 2 more evaluation assessments. Aggregate data blinded to outcomes will be used to assess patient accrual, treatment protocol compliance, and separation of intravenous fluid and/or vasopressor administration. Protocol adjustments may be made at each of these patient marks to optimize the protocol. The study may be halted during the feasibility assessment phase for failure to meet pre-specified stopping guidelines
3. Trial progress will be evaluated by an independent Data and Safety Monitoring Board (DSMB) to determine whether the study should stop for superiority of either the liberal or restrictive fluid strategies; or, for projected trial futility. (See Appendix B) There will be two interim analyses and a final analysis conducted when approximately each successive 1/3 of the patients have been enrolled.

3. Trial Description

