9.1 Sample Size and Stopping Rules for Primary Outcome

The primary outcome is intention-to-treat 90-day all cause in-hospital mortality, where in-hospital includes both study and discharge hospitals (i.e. transfer hospitals or LTAC). Subjects who are discharged home (defined as residence prior to admission) prior to day 90 will be assumed to be alive at day 90.

Sample size is based on a comparison of binomial proportions with an overall two-sided alpha level of 0.05 and power of 0.90. With 15% mortality rate in liberal fluid group and 10.5% mortality rate in the restrictive group, maximum required total sample size is 2320 subjects.

The presumed 15% mortality rate in the liberal fluid group is based on several recently published clinical trials (Process [2], ARISE [3], Promise [4]).

This trial will stop for efficacy of either the restrictive or liberal fluid strategy arm, or futility. The study is designed with a symmetric group sequential t^4 alpha error spending function and a symmetric non-binding t^4 beta error spending function, where t is the information time, defined as the ratio of the effective sample size at the time of the look to the eventual sample size.

We plan to have two interim analyses and one final analysis that will be approximately evenly spaced. However, the scheduling of the DSMB meetings may alter this schedule.

Tables 1 and 2 present the stopping boundaries at each of the two interim analyses if they are equally spaced. The tables present stopping boundaries as either a one-sided p-value or an observed mortality difference. Table 3 presents the probability of stopping at each stage under the null (no effect of fluid) and alternative (restrictive fluid reduces mortality from 15% to 10.5%) hypotheses respectively.

Table 1. Stopping Boundaries: One Sided P Values

Stage	Sample Size	Lower Efficacy	Lower Futility	Upper Futility	Upper Efficacy
1	773	0.0003086	.	.	0.99969
2	1547	0.00479	0.27413	0.72587	0.99521
3	2320	0.02361	0.02361	0.97639	0.97639

Table 2. Stopping Boundaries: Mortality Differences

Stage	Sample Size	Lower Efficacy	Lower Futility	Upper Futility	Upper Efficacy
1	773	-0.08194	.	.	0.08194
2	1547	-0.04384	-0.01016	0.01016	0.04384
3	2320	-0.02742	-0.02742	0.02742	0.02742

Table 3. Cumulative Stopping Probabilities

Stage	Stop: Reject Null Given Null	Stop: Accept Null Given Null	Stop: Reject Null Given Alternative	Stop: Accept Null Given Alternative
1	0.00062	0.00000	0.06136	0.00000
2	0.00988	0.45174	0.52878	0.01919

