13.1 Safety Monitoring

Assuring patient safety is an essential component of this protocol. Each participating investigator has primary responsibility for the safety of the individual participants under his or her care. The Investigators will determine daily if any adverse events occur during the period from enrollment through **study day 6** (five days after completion of the study fluid protocol) or Hospital discharge, whichever occurs first.

The following adverse events will be collected in the adverse event case report forms:

- Serious adverse events
- Non-serious adverse events that are considered by the investigator to be related to study procedures or of uncertain relationship (Appendix G)

A clinical trial adverse event is any untoward medical event associated with study procedures, whether or not it is considered related to the study procedures.

After randomization, adverse events must be evaluated by the investigator. If the adverse event is judged to be reportable, as outlined above, then the investigator will report to the CCC their assessment of the potential relatedness of each adverse event to protocol procedure via electronic data entry. Investigators will assess if there is a reasonable possibility that the study procedure caused the event, based on the criteria outlined in Appendix G. Investigators will also

consider if the event is unanticipated or unexplained given the patient's clinical course, previous medical conditions, and concomitant medications.

Determining whether a treatment is causally related to the development of increased oxygen requirements is a challenge, as it is difficult for a clinician to reliably discern hydrostatic from non-hydrostatic pulmonary edema. Furthermore, increased hypoxia and/or need for additional respiratory support may be due to disease progression (eg early phases of ARDS) or a fluid bolus and this is also difficult to discern. We will not consider the study endpoints of use of high-flow nasal cannula, non-invasive ventilation, or endotracheal intubation as AEs unless the events are judged by the investigator to be related to study procedures (see Appendix G2).

If a patient's treatment is discontinued as a result of an adverse event, study site personnel must report the circumstances and data leading to discontinuation of treatment in the adverse event case report forms.

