Serious adverse events will be collected during the first **6 study days** or until ICU discharge, whichever occurs first, regardless of the investigator's opinion of causation. Thereafter, serious adverse events are not required to be reported unless the investigator feels the events were related to either study drug or a protocol procedure.

Appendices

[figure not shown]
A. Protocol Schema

¹ extreme hypovolemia defined as IVC < 5mm, empty left ventricle; Volume responsiveness by any measure > 30%

[figure not shown]
A.1 Liberal Protocol (follow for 24 hours)

Liberal Arm Flow Chart (follow for 24 hours)

Fluid Liberal Flowchart

A.2 Restrictive Protocol (follow for 24 hours)

^AEpinephrine suggested, but not mandated, as second vasopressor

^BNorepinephrine 20mcg/min or 0.25 mcg/kg/min

^CDefined as: maximal IVC diameter < 5mm; or Empty left ventricle on echo (e.g. left-ventricular end-diastolic area index < 5.5 cm²/m² BSA) or Substantial volume responsiveness defined as stroke volume increase > 30% in response to a passive leg raise, fluid challenge, or positive pressure breaths

B. Data and Safety Monitoring Board

The principal role of the DSMB is to assure the safety of patients in the CLOVERS trial. They will regularly monitor data from this trial, review and assess the performance of its operations, and make recommendations to the NHLBI with respect to:

- Review of adverse events
- Interim results of the study for evidence of efficacy or adverse events
- Possible early termination of the trial because of early attainment of study objectives, safety concerns, or inadequate performance
- Possible modifications in the clinical trial protocol
- Performance of individual centers

Two interim analyses will be conducted at approximately 33% and 66% target enrollment accrual.

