As noted in section 11.2, investigators will report all adverse events that are serious and study procedure related (or of uncertain relatedness) to the CCC within 24 hours. The CCC will then notify the NHLBI and Central Institutional Review Board (cIRB)

The Medical Monitor at the CCC will work collaboratively with the reporting investigator to determine if a serious adverse event has a reasonable possibility of having been caused by the study procedure, as outlined in 21 CFR 312.32(a)(1), and below. The Medical Monitor will also determine if the event is unexpected. An adverse is considered “unexpected” if it is not listed in the study protocol (21 CFR 312.32(a)). If a determination is made that a serious adverse event has a reasonable possibility of having been caused by the study procedure, it will be classified as a suspected adverse reaction. If the suspected adverse reaction is unexpected, it will be classified as a serious unexpected suspected adverse reaction (SUSAR).

The CCC will report all unexpected deaths, serious and treatment related adverse events, and SUSARs to the DSMB, NHLBI, and cIRB within 7 days after receipt of the report from a clinical site. A written report will be sent to the NHLBI, DSMB and the cIRB within 15 calendar days. The DSMB will also review all adverse events and clinical outcomes during scheduled interim analyses. If the DSMB determines that the overall rate of adverse events is higher in one fluid protocol group, the cIRB will be notified within 15 days of this determination. The CCC will distribute the written summary of the DSMB’s periodic review of adverse events to the cIRB in accordance with NIH guidelines (<http://grants.nih.gov/grants/guide/notice-files/not99-107.html>).

G1. Unanticipated problems (UP)

Investigators must also report Unanticipated Problems, regardless of severity, associated with study procedures within 24 hours. An unanticipated problem is defined as follows: any incident, experience, or outcome that meets all of the following criteria:

- Unexpected, in terms of nature, severity, or frequency, given the research procedures that are described in the protocol-related documents, such as the IRB-approved research protocol and informed consent document; and the characteristics of the subject population being studied;

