- Related or possibly related to participation in the research, in this guidance document, possibly related means there is a reasonable possibility that the incident, experience, or outcome may have been caused by the procedures involved in the research;
- Suggests that the research places subjects or others at a greater risk of harm (including physical, psychological, economic, or social harm) than was previously known or recognized.

G2. Determining relationship of adverse events to procedures

Investigators will be asked to grade the strength of the relationship of an adverse event to study procedures as follows:

- **Definitely Related:** The event follows: a) A reasonable, temporal sequence from a study procedure; and b) Cannot be explained by the known characteristics of the patient's clinical state or other therapies; and c) Evaluation of the patient's clinical state indicates to the investigator that the experience is definitely related to study procedures.
- **Probably or Possibly Related:** The event should be assessed following the same criteria for "Definitely Associated". If in the investigator's opinion at least one or more of the criteria are not present, then "probably" or "possibly" associated should be selected.
- **Probably Not Related:** The event occurred while the patient was on the study but can reasonably be explained by the known characteristics of the patient's clinical state or other therapies.
- **Definitely Not Related:** The event is definitely produced by the patient's clinical state or by other modes of therapy administered to the patient.
- **Uncertain Relationship:** The event does not meet any of the criteria previously outlined.

[figure not shown]
G3. Clinical outcomes that may be exempt from adverse event reporting

Study-specific clinical outcomes of sepsis, as outlined in Sections 3.8.1 and 3.8.2 (Primary and Secondary Outcomes) and Section 6.3 (Assessments During the Study) are exempt from adverse event reporting unless the investigator deems the event to be related to the study procedures (or of uncertain relationship) or if the event leads to discontinuation of study procedures. The following are examples of events that will be considered study specific clinical outcomes

- Death not related to the study procedures.

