### Adverse Events

Adverse events will be analyzed using weighted Poisson regression with non-serious events weighted by one and serious events weighted by two. Events rather than patients will be the unit of analysis. Adverse events will be grouped and analyzed separately by MedDRA system organ classes.

The analysis is intention to treat and significance testing will be two-tailed at  $\alpha = 0.05$  with no adjustment made for multiple comparisons.

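### Non-serious and Appendix G3 events reach the adverse event data mainly through a relatedness call made with knowledge of the arm, yet the SAP tests the recorded counts at 0.05; if attribution differs by arm, equal incidence can test as different

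*Protocol*

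**What the plan says.** Protocol 2.4 describes a "phase 3 randomized non-blinded interventional trial of fluid treatment strategies", so whoever decides whether an event is recorded knows the arm.

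The recording rules differ by type of event:

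- **Serious events.** Protocol 13.1 lists them with no relatedness condition. Section 13.2 collects them over the first six study days, or to ICU discharge, "regardless of the investigator's opinion of causation".
- **Non-serious events.** Section 13.1 collects "Non-serious adverse events that are considered by the investigator to be related to study procedures or of uncertain relationship".
- **Respiratory support.** Section 13.1 counts high-flow oxygen, non-invasive ventilation and intubation as adverse events only if the investigator considers them related to study procedures.
- **Appendix G3 outcomes.** Cardiovascular, respiratory, hepatic, renal and coagulation events, and deaths unrelated to procedures, "are exempt from adverse event reporting unless the investigator deems the event to be related to the study procedures (or of uncertain relationship"), or unless the event stops study procedures.

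The SAP Adverse Events section uses Poisson regression with weight one for non-serious and two for serious events, and counts events rather than patients. It states: "Adverse events will be grouped and analyzed separately by MedDRA system organ classes". Testing is intention to treat, two-tailed at 0.05 and unadjusted. The recording rules are not mentioned.

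Appendix G adds a notification: "If the DSMB determines that the overall rate of adverse events is higher in one fluid protocol group", the central IRB is told within 15 days.

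**The concern.** A between-arm test of event counts assumes that an event has the same chance of being recorded in either arm. Here, for non-serious and G3 events, that chance depends mainly on an investigator's opinion of cause, formed with the allocation known.

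The protocol gives reasons why that opinion could differ by arm. Section 11.1 lists fluid overload and breathing difficulty as risks of fluid, and ischemia and dysrhythmia as risks of vasopressors. Section 13.1 concedes that a clinician cannot easily tell worsening hypoxia due to a fluid bolus from disease progression. Appendix G2 grades relatedness partly on timing after a study procedure, and the procedures differ by arm. A respiratory event may therefore be called related more readily in the liberal arm, and an arrhythmia more readily in the restrictive arm.

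The SAP's Null Hypothesis section does not cover this. It defends the Type I error rate for outcomes defined only in patients still on study, where the problem is differential recovery and survivorship. What is at stake is whether a difference by system organ class is read as a treatment harm, or its absence as reassurance, when it reflects recording.

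**Working it through.** **Inputs from the documents.** Protocol 2.11: "Randomization 1:1; two-sided alpha 0.05". Protocol 9.1: "With 15% mortality rate in liberal fluid group and 10.5% mortality rate in the restrictive group, maximum required total sample size is 2320 subjects". The SAP supplies the weights (1 and 2) and the 0.05 level.

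**Reproducing the plan's figure.** n per arm = [1.960·√(2·0.1275·0.8725) + 1.2816·√(0.15·0.85 + 0.105·0.895)]² / 0.045² = 1,153, or 2,306 in total. That is within 1% of 2,320, and 1,160 per arm gives power 0.902. So 1,160 per arm is used below. The plan states no adverse event rate or power to reproduce.

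**Assumed, because the documents give no figure.** True incidence of the filtered events is 10% (also 20%), equal in both arms. The probability that an event is called related or uncertain is q1 in one arm and q2 in the other.

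**Step 1: a class holding filtered events only.** The expected recorded count is 1,160 × incidence × q. The test is z = (X1 − X2)/√(X1 + X2), rejecting at |z| > 1.96, with simulated Poisson counts.

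| q1 v q2 | Expected counts at 10% incidence | Rejection at 10% | Rejection at 20% |
|---|---|---|---|
| 5% v 5% | 5.8 v 5.8 | 4% | 5% |
| 5% v 10% | 5.8 v 11.6 | 29% | 51% |
| 5% v 15% | 5.8 v 17.4 | 71% | 94% |
| 5% v 20% | 5.8 v 23.2 | 93% | over 99% |

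Smaller gaps do little at 10% incidence: 5% v 6% rejects in 5.5% of trials and 5% v 7.5% in 11%.

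Higher attribution with a smaller ratio gives a similar picture. At 0.1 events per patient and q of 20% v 30%, expected counts are 23.2 and 34.8. A Wald test has log(1.5) = 0.405 and standard error √(1/23.2 + 1/34.8) = 0.268, so the expected z is 1.51 and rejection is 33%. For 20% v 25% it is 13%, and for 20% v 40% it is 78%.

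**Step 2: add unfiltered serious events at weight two.** Assume 0.02 serious events per patient in the class, equal in both arms, so 23.2 per arm. The weighted total is W = a + 2c, where a is filtered non-serious and c is serious events. The robust variance of log W is (a + 4c)/W². At 10% incidence and q1 = 5%, W1 = 5.8 + 46.4 = 52.2.

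| q2 | W2 | W2/W1 | log ratio / SE | Rejection |
|---|---|---|---|---|
| 10% | 58.0 | 1.11 | 0.105 / 0.259 = 0.41 | 7% |
| 15% | 63.8 | 1.22 | 0.201 / 0.252 = 0.80 | 13% |
| 20% | 69.6 | 1.33 | 0.288 / 0.245 = 1.17 | 22% |

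With 0.05 serious events per patient, the three figures are about 6%, 8% and 12%.

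Robust variance is used to isolate the attribution effect. The SAP names no variance estimator. With model-based variance, the weighting alone gave about 13% to 16% rejection under equal attribution in the simulated cases, which is a separate matter.

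**The case against.** The strongest reply is that the plan does not depend on the adverse event table for these outcomes. SAP 1.9 compares ventilation, renal replacement, arrhythmia, ICU admission, oxygen use, KDIGO stage, SOFA and mortality with no relatedness filter. Protocol 7.2 sends oxygen support and signs of fluid overload to the DSMB at least quarterly. This stands, and it confines the problem to the adverse event table. It is weakest for hepatic and coagulation events, which have little other capture beyond SOFA at 72 hours.

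A second reply is that the size rests on assumption. This also stands. Attribution rates are unknown, small gaps cause little inflation, and unfiltered serious events dilute it sharply. Differential attribution is well supported for respiratory and arrhythmia events; section 11.1 lists no arm-specific hepatic, renal or coagulation risk. Because uncertain relationship is itself reportable, hard-to-attribute events can enter from both arms.

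A reader might infer four stronger things that the documents do not support:

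- **That filtered events are recorded only when blamed on study procedures.** Uncertain relationship also qualifies, as does stopping procedures for G3 events. Both routes remain open to influence from knowing the arm.
- **That every G3 event is filtered.** For serious ones this is unsettled, because sections 13.1 and 13.2 collect serious events without a causality condition while G3 exempts the listed outcomes.
- **That the 5% level fails outright.** With equal attribution it holds.
- **That the IRB notification is triggered by a biased 0.05 test.** Appendix G describes a DSMB determination, made with clinical outcomes also in view.

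**Conclusion.** The point holds in a limited form. Recording of non-serious and G3 events depends mainly on a relatedness call by someone who knows the arm. The SAP tests the recorded counts as if they measured incidence, and nothing in either document addresses this.

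The 5% level may fail for classes dominated by filtered events, and it fails only if attribution differs by arm. Two- to four-fold attribution gaps at 10% incidence give about 29% to 93% rejection in a class with filtered events alone. With 0.02 unfiltered serious events per patient, weight two and robust variance, the range is about 7% to 22%. These figures illustrate the mechanism and are not estimates for this trial. The same mechanism can mask a true difference.

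The consequence is a misleading adverse event table rather than compromised safety evidence overall. The change is worth making because it needs only wording.

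**What to change.** 1. **SAP Adverse Events section.** Restrict formal between-arm tests to serious events collected regardless of causation. List non-serious and exempt-unless-related events by arm, seriousness and relatedness grade, without p-values.
2. **G3 event types.** Refer to the endpoints already compared without a relatedness filter: SAP 1.9 items 7 to 11, 13, 14a to 14d, 14f and 14m. These include KDIGO stage, and SOFA with its bilirubin and platelet components. Note that ARDS (items 12 and 14e) does not escape the problem, because local unblinded investigators must decide whether heart failure or fluid overload fully accounts for the hypoxemia.
3. **Define the tested set.** Reconcile section 13.2, which collects serious events regardless of causation, with the G3 exemption. Reconcile the hospital-discharge end of collection in 13.1 with the ICU-discharge end in 13.2.
4. **Appendix G.** Leave the IRB notification in place, so that procedure-related events still count toward it, but show the DSMB filtered and unfiltered events separately.

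The cost is wording in the SAP and protocol, with no new data collection. There will be fewer p-values in the adverse event table, and non-serious related events will be described rather than tested.
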